4.7. Dosing Delays and Modification for Toxicity

4.7.1. Management of Cytokine Release Syndrome (CRS)/Infusion-related reactions (IRR)

In the first weeks of treatment, patients are at risk for cytokine release syndrome (CRS) and infusion-related reactions (IRR). While these reactions occur in the majority of patients treated with flotetuzumab (81%), most events are either grade 1 or 2. The severity of these events seems to correlate with the baseline absolute CD3+ T cell count and increasing cytokine levels, especially interleukin-6 (IL-6). The risk of CRS was decreased with two-step lead-in dosing.⁶⁴ Due to the relationship between IL-6 levels and the severity of CRS, an early intervention strategy with the IL-6 receptor antagonist tocilizumab was used to mitigate toxicity in the phase I trial. CRS/IRR should be graded according to the ASTCT CRS Consensus Grading System⁶⁵

Table 4 ASTCT CRS Consensus Grading⁶⁵

Table 2
 ASTCT CRS Consensus Grading

CRS Parameter	Grade 1	Grade 2	Grade 3	Grade 4
Fever*	Temperature $\geq 38^{\circ}\text{C}$	Temperature $\geq 38^{\circ}\text{C}$	Temperature $\geq 38^{\circ}\text{C}$	Temperature $\geq 38^{\circ}\text{C}$
With				
Hypotension	None	Not requiring vasopressors	Requiring a vasopressor with or without vasopressin	Requiring multiple vasopressors (excluding vasopressin)
And/or [†]				
Hypoxia	None	Requiring low-flow nasal cannula [‡] or blow-by	Requiring high-flow nasal cannula [‡] , facemask, nonbreather mask, or Venturi mask	Requiring positive pressure (eg, CPAP, BiPAP, intubation and mechanical ventilation)

Organ toxicities associated with CRS may be graded according to CTCAE v5.0 but they do not influence CRS grading.

* Fever is defined as temperature $\geq 38^{\circ}\text{C}$ not attributable to any other cause. In patients who have CRS then receive antipyretic or anticytokine therapy such as tocilizumab or steroids, fever is no longer required to grade subsequent CRS severity. In this case, CRS grading is driven by hypotension and/or hypoxia.

† CRS grade is determined by the more severe event: hypotension or hypoxia not attributable to any other cause. For example, a patient with temperature of 39.5°C , hypotension requiring 1 vasopressor, and hypoxia requiring low-flow nasal cannula is classified as grade 3 CRS.

‡ Low-flow nasal cannula is defined as oxygen delivered at ≤ 6 L/minute. Low flow also includes blow-by oxygen delivery, sometimes used in pediatrics. High-flow nasal cannula is defined as oxygen delivered at >6 L/minute.

Table 5 Definition of High Dose Vasopressor

Pressor	High Dose (doses less than these would be considered Low Dose)
Norepinephrine monotherapy	$\geq 20 \mu\text{g}/\text{min}$
Dopamine monotherapy	$\geq 10 \mu\text{g}/\text{kg}/\text{min}$
Phenylephrine monotherapy	$\geq 200 \mu\text{g}/\text{min}$
Epinephrine monotherapy	$\geq 10 \mu\text{g}/\text{min}$
If on vasopressin	Vasopressin + norepinephrine equivalent of $\geq 10 \mu\text{g}/\text{min}^*$
If on combination vasopressors (not vasopressin)	Norepinephrine equivalent of $\geq 20 \mu\text{g}/\text{min}^*$

The above grading scale should be used to grade all infusion reactions in this study, irrespective of the underlying mechanism of the reaction. Certain AEs may occur in temporal proximity to infusion of study drug and therefore, be considered “infusion-related” while not being considered an “infusion reaction;” such events may be graded separately according to CTCAE specific criteria version 5.

IRR/CRS should be managed as described below. Every attempt should be made to continue the infusion during management of the reaction.

Table 6 CRS Severity and Management

CRS Severity	Management


Non-life-threatening
 
 • Fever • Tachycardia • Nausea • Fatigue • Headache • Malaise • Myalgias 	
 ○ Slow the infusion rate by 10-20%. ○ Monitor the patient for worsening of condition. ○ Administer IV fluids, diphenhydramine hydrochloride (or institutional equivalent) 50 mg IV, acetaminophen 1000 mg PO or ibuprofen 400 mg PO for fever, and oxygen and bronchodilators for mild bronchospasm, as appropriate; ○ Administer tocilizumab (4-8 mg/kg IV) if the above symptoms do not resolve within 2 hours with supportive therapy, or is associated with any of the following signs and symptoms: 
 ▪ Temperature > 101.5oF (38.6oC) ▪ Signs of pending respiratory compromise as indicated by RR > 20/min ▪ HR > 20 bpm above pre-treatment baseline ▪ Note: isolated changes in hemodynamic parameters alone that do not require intervention without pulmonary compromise or fever should not prompt immediate use of tocilizumab. ○ Corticosteroids should not be used. ○ Continue infusion at reduced rate and slowly increase infusion rate to the original rate in 2 steps after stabilization or resolution of symptoms every 4-6 hours, as tolerated. A more gradual increase in the rate of infusion may be undertaken after consultation with the Principal Investigator.

Requiring mild intervention defined by
 
 • Decreases in BP requiring fluid boluses or low-dose vasopressors, requiring supplemental oxygen (≤ 6 L/min by supplemental oxygen) to maintain oxygen saturation >92%, or • Grade 2 organ toxicity 	
 ○ Slow the infusion rate by 25-50%. ○ Administer IV fluids, diphenhydramine hydrochloride 50 mg IV or institutional equivalent, acetaminophen 1000 mg PO or ibuprofen 400 mg PO for fever, and oxygen and bronchodilators for bronchospasm, as appropriate and if not administered previously; ○ Administer vasopressors (at doses < 20 ng/min of norepinephrine) as needed for circulatory support. ○ Tocilizumab (8 mg/kg IV) should be used for the above signs if they do not resolve with other measures within 2 hours, or that requires the use of supplemental oxygen > 4 L by nasal cannula or low dose vasopressors.

	
 ○ Corticosteroids may be used for patients that do not respond to other measures, including tocilizumab. ○ Continue infusion at reduced rate and slowly increase infusion rate to the original rate gradually by half-rate increments (i.e. if rate is reduced from 5 mL/hr to 2.5 mL/hr increase to ~3.75 mL/hr, then 4.25 mL/hr, then 5 mL/hr) after stabilization or resolution of symptoms every 4-6 hours, as tolerated. A more gradual increase in the rate of infusion may be undertaken after consultation with the principal investigator. ○ Report the event as a serious adverse event (SAE), if appropriate. ○ Monitor for worsening condition;
Life threatening defined by	
 ○ Stop the infusion. ○ TO AVOID EXACERBATION OF INFUSION REACTION OR CRS: DO NOT FLUSH THE TUBING – ASPIRATE RESIDUAL DRUG FROM THE PORT LUMEN. ○ Administer IV fluids, diphenhydramine hydrochloride (or institutional equivalent) 50 mg IV, acetaminophen 1000 mg PO or ibuprofen 400 mg PO for fever, and oxygen and bronchodilators for mild bronchospasm, as appropriate. ○ Provide appropriate circulatory support including vasopressors as medically indicated; ○ Administer tocilizumab if not administered previously. If administered previously, an additional dose may be used for prolonged or recurrent episodes. ○ Symptoms that are refractory to tocilizumab should be treated with any of the following: 
 ▪ Corticosteroids; doses of dexamethasone (or equivalent) of greater than 30 mg may be required ▪ Etanercept (or equivalent anti-TNFα) 50 mg IV, and/or daclizumab (anti-IL2 receptor) 1 mg/kg IV (where approved); ○ Resume the infusion at previously tolerated dose once the infusion reaction has resolved or decreased to Grade 1. Increase dose rate to the original rate, as prescribed by protocol, e.g., 500 ng/kg/day, by increasing the dose in near double

	
increments as tolerated after stabilization or resolution of symptoms every 4-6 hours. A more gradual increase in the rate of infusion may be undertaken after consultation with the Principal Investigator.
 
○ Report the event as a serious adverse event (SAE), if appropriate.○ Discontinue the infusion if not resolved to Grade 1 within 72 hours.
Resulting in death	
○ Notify the regulatory authorities.○ Report the event as an SAE.

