6.2.2. Infusion-related Reaction

Infusion-related reaction including cytokine release syndrome (CRS), which may be life-threatening or fatal, occurred in 81% of patients receiving flotetuzumab. The majority of these reactions were mild to moderate in severity, whereas 8% of patients treated at the RP2D experienced at least one severe (Grade 3) event. None of these events have been life threatening or fatal. Infusion reactions may be clinically indistinguishable from manifestations of

CRS. This typically occurs during the initial 48 hours of the first infusion of flotetuzumab. Symptoms of infusion-related reactions including CRS may include chills, fever, headache, fatigue, flushing, nausea, bronchospasm, and hypotension. Patients should be closely monitored for signs or symptoms of these events. For all patients receiving inpatient flotetuzumab infusion, vital signs should be monitored according to the inpatient standard-of-care. Management of these events may require either temporary interruption or discontinuation of flotetuzumab as described in Section [4.5.1](#).

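### Table 6's mild-intervention row limits vasopressors by dose but not by number, so its slow-and-continue instruction takes in CRS that Table 4 grades as Grade 4

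*Combined protocol and SAP*

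**What the plan says.** Section 4.7.1 uses three tables.

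- **Table 4** grades CRS hypotension by number of agents. One pressor, with or without vasopressin, is Grade 3. Grade 4 is "Requiring multiple vasopressors (excluding vasopressin"). The footnote's worked example confirms that the count decides: "hypotension requiring 1 vasopressor, and hypoxia requiring low-flow nasal cannula is classified as grade 3 CRS". The text after Table 5 applies this scale to all infusion reactions in the study.
- **Table 5** sorts regimens by dose, and anything under its thresholds is low dose. One line reads "If on combination vasopressors (not vasopressin"), with high dose starting at 20 µg/min norepinephrine equivalent. Vasopressin plus another pressor has its own line, with high dose from 10 µg/min norepinephrine equivalent.
- **Table 6** gives the management. The mild-intervention criterion includes "Decreases in BP requiring fluid boluses or low-dose vasopressors". Its pressor instruction is "Administer vasopressors (at doses < 20 ng/min of norepinephrine) as needed for circulatory support". The infusion is slowed by 25-50%, and then: "Continue infusion at reduced rate and slowly increase infusion rate to the original rate gradually by half-rate increments". The life-threatening row stops the infusion and clears the line. It then says "Resume the infusion at previously tolerated dose once the infusion reaction has resolved or decreased to Grade 1", and it discontinues the drug if Grade 1 is not reached within 72 hours.

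Two other sections bear on Grade 4 CRS. Section 6.2.1 exempts only Grade 3 CRS that resolves within 72 hours from being a DLT, on the ground that it does not call for permanent discontinuation. Section 4.7.4 permanently discontinues flotetuzumab after a related Grade 4 non-hematological event.

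**The concern.** CRS is the drug's main toxicity, and Table 6 is the bedside instruction for it. If the mild row admits a patient already at Grade 4, a clinician who follows that row keeps the drug running and may raise the rate once the patient has stabilized. Unlike the life-threatening row, the mild row has no requirement to reach Grade 1 and no 72-hour limit. The text before Table 6 also asks staff to keep the infusion going wherever possible, which pushes an unclear case toward continuing. What is at stake is the safety of an individual patient and the consistency of treatment between clinicians. The trial's estimates are not at stake.

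**Working it through.** The plan states no figure to reproduce, so the check sets the three tables side by side for a patient with fever attributed to CRS.

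| Support needed for hypotension | Table 4 (count) | Table 5 (dose) | Within the mild row's wording? |
|---|---|---|---|
| Fluids only | Grade 2 | not applicable | yes |
| One pressor, low dose | Grade 3 | low | yes |
| One pressor plus vasopressin, norepinephrine equivalent < 10 µg/min | Grade 3 | low | yes |
| Two or more non-vasopressin pressors, total norepinephrine equivalent < 20 µg/min | **Grade 4** | low | **yes** |

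**Illustration (doses assumed).** Norepinephrine at 8 µg/min plus a second agent worth 4 µg/min gives 8 + 4 = 12 µg/min, which is below 20. That regimen is low dose by Table 5, mild by Table 6 and Grade 4 by Table 4.

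**The management line does not close the gap.** It caps the norepinephrine dose and says nothing about a second agent. Its unit appears as ng/min, against µg/min in Table 5, a ratio of 20 µg / 20 ng = 1,000. Read in either unit, it limits dose and not count.

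**The row's other limbs stop lower.** Oxygen up to 6 L/min matches Table 4's low-flow definition (Grade 2 by nasal cannula), and organ toxicity stops at Grade 2. Only the blood-pressure limb reaches Grade 4.

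**What the two rows deliver.** Slowing by 25-50% leaves 0.50 to 0.75 of the rate. The stop row leaves 0.

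- Full dose, DL1: 0.50 × 500 = 250 to 0.75 × 500 = 375 ng/kg/day.
- Full dose, DL-1: 0.50 × 300 = 150 to 0.75 × 300 = 225 ng/kg/day.
- Early lead-in: section 6.2.2 says of these reactions, "This typically occurs during the initial 48 hours of the first infusion of flotetuzumab". Table 1 is broken in the text. Reading it as 30 ng/kg/day on Day 1 and 60 on Day 2 (an assumption that agrees with section 4.2's 500 from day 7) gives 15-22.5 on Day 1 and 30-45 on Day 2.

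**Which rule governs Grade 4 CRS.** The visible text offers up to three answers:

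1. The mild row slows and continues.
2. The life-threatening row stops and resumes at Grade 1. Whether it names multiple pressors cannot be read.
3. Section 4.7.4 discontinues permanently, if it reaches CRS. Its heading concerns other adverse events, but its text makes no exception for CRS.

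The first answer is also at odds with section 6.2.1, whose reason for the exemption (no need for permanent discontinuation) is given for Grade 3 only.

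**The case against.** The best defence is that two schemes coexist on purpose, with grading by number of agents and management by dose. Table 5's combination line has no visible use other than sorting multi-pressor patients for Table 6, which suggests intent. This stands in part. A dose-based rule is legitimate, and treating single-pressor Grade 3 CRS in the mild row is coherent. But the protocol makes Table 4 the scale for every infusion reaction and nowhere says that some Grade 4 CRS is meant to be managed as mild.

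The second objection is that the cell defining life-threatening CRS cannot be read and may name multiple pressors. This stands as a limit on the consequence. It does not narrow the mild row, because the same patient would then fit a continue row and a stop row together. A reader might infer that the protocol has no stop instruction for Grade 4 CRS. The documents do not support that, both because of the unreadable cell and because of section 4.7.4.

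The third objection is that harm is limited, and this stands. The mild row calls for tocilizumab 8 mg/kg when low-dose pressors are needed, allows corticosteroids if other measures fail, ties rate increases to stabilization or resolution, and asks for monitoring of worsening. Section 6.2.2 reports no life-threatening or fatal reactions so far.

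A reader might also turn the absence of Grade 4 infusion reactions among the 66 patients in section 6.2.3 into an upper limit on the rate. That is not supported. The section does not say which CRS scale was used, so a patient on two low-dose pressors might not have been recorded as Grade 4.

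**Conclusion.** The point holds as a minor one. Confidence is high that the mild row's wording overlaps Table 4 Grade 4, and moderate on the bedside consequence, which depends on the unreadable cell and on whether section 4.7.4 applies to CRS. For an affected patient the difference is 50-75% of the assigned rate against none. The overlap is confined to combinations of non-vasopressin agents below 20 µg/min norepinephrine equivalent. The event is probably rare, but the documents give no usable rate for it and none after alloHSCT.

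A reader might infer that the DLT count or the MTD is distorted. Neither is, because section 6.2.1 takes the CRS grade from Table 4 whichever row was used for management. Nor can a 1,000-fold dosing error be claimed from the ng/min unit, which may come from the reading of the PDF.

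**What to change.** By amendment to section 4.7.1, Table 6:

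1. In the mild row's criterion, replace the reference to low-dose vasopressors with: *one low-dose vasopressor, or one vasopressor plus vasopressin below Table 5's vasopressin threshold; multiple non-vasopressin pressors (Table 4 Grade 4) are managed in the life-threatening row*.
2. In that row's management line, replace the norepinephrine limit with: *one agent, low dose as defined in Table 5, with or without vasopressin*. This also settles the unit.
3. Confirm that the life-threatening row lists Table 4 Grade 4 hypotension, and add it only if absent. State whether section 4.7.4's permanent discontinuation or Table 6's resumption at Grade 1 governs Grade 4 CRS.

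Tables 4 and 5 and section 6.2.1 stay as they are. If the sponsor does want dose to override the number of agents, it should say openly that some Grade 4 CRS is managed with the infusion running.

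The cost is two phrases, one check and one clarifying sentence, with no added visits, staff or patients. The downside is that a rare patient on two low-dose pressors has the infusion stopped (or discontinued, if section 4.7.4 governs), and Table 5's combination line no longer decides a row in the visible text.

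### The Table 6 mild-intervention row limits norepinephrine to below 20 ng/min, where Table 5 puts the low-dose boundary at 20 micrograms/min: a 1000-fold unit mismatch, minor in effect, to be confirmed in the source PDF

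*Combined protocol and SAP*

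**What the plan says.** Section 4.7.1 of the combined protocol and SAP contains both tables.

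- **Table 5** defines high-dose vasopressor use. Its column heading reads "High Dose (doses less than these would be considered Low Dose", so low dose means anything under the listed values. The entry for norepinephrine monotherapy is 20 micrograms/min or more. All six thresholds are in micrograms.
- **Table 6** gives CRS management by severity. One entry criterion for the row on mild intervention is "Decreases in BP requiring fluid boluses or low-dose vasopressors". The treatment bullet in that row is "Administer vasopressors (at doses < 20 ng/min of norepinephrine) as needed for circulatory support". The next bullet sets out when tocilizumab should be used and returns to the same dose category: "or that requires the use of supplemental oxygen > 4 L by nasal cannula or low dose vasopressors".
- The **life-threatening row** of Table 6 sets no number: "Provide appropriate circulatory support including vasopressors as medically indicated".

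**The concern.** The low-dose category appears on both sides of the disputed bullet, in the entry criterion and in the tocilizumab trigger. Table 5 is the only place that defines it. The bullet names a drug that Table 5 lists and uses the number that Table 5 gives for it, but in nanograms. No section explains a separate, much lower limit for norepinephrine in this row.

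The bullet is an operative treatment instruction for hypotensive patients with CRS. If the limit is wrong as written, staff following Section 4.7.1 meet two incompatible figures for one drug in adjoining tables. What is at stake is the clarity of a safety instruction, not a statistical quantity.

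**Working it through.** The check is a unit conversion followed by a comparison of the two tables.

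**Inputs**
- Table 6, mild-intervention row: norepinephrine below 20 ng/min.
- Table 5, norepinephrine monotherapy: high dose from 20 micrograms/min, so low dose is below 20 micrograms/min.
- Conversion: 1 ng is one thousandth of a microgram, as Section 6.1 (item 8, dose preparation) states in words.

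**Step 1. Table 5 boundary in ng/min.** 20 micrograms/min × 1000 ng per microgram = 20,000 ng/min.

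**Step 2. Table 6 limit in micrograms/min.** 20 ng/min ÷ 1000 = 0.02 micrograms/min.

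**Step 3. Ratio.** 20,000 ÷ 20 = 1000. The Table 6 limit is 20 ÷ 20,000 = 0.1% of the Table 5 boundary.

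**Step 4. Doses caught between the two.** Any dose from 0.02 to just under 20 micrograms/min is low dose under Table 5 but outside the Table 6 bullet. For example, 5 micrograms/min is low dose by Table 5, yet it is 5,000 ÷ 20 = 250 times the figure in the bullet.

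**Step 5. Effect of correcting the unit.** With micrograms in place of ng, Table 6 reads below 20 micrograms/min. That equals the Table 5 low-dose limit for norepinephrine monotherapy exactly (20 ÷ 20 = 1).

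**Step 6. Does anything statistical depend on it?** Table 4 grades hypotension in CRS by whether a vasopressor is needed and whether more than one is needed, not by dose. The DLT definition in Section 6.2.1 uses that grading for CRS. The 3+3 rules and the expansion-cohort stopping rule in Section 8.2 count DLTs. The vasopressor dose enters none of these.

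**The case against.** **It may be a reading artefact.** The text was read from PDF, and special characters did fail in Table 6 itself: the degree signs appear as the letter o in "Temperature > 101.5oF (38.6oC". Section 6.1 also prints mg as the symbol for microgram, so the microgram sign is wrong in at least one other place. On the other side, Table 5 shows its micro signs correctly and Table 6 keeps the Greek letter in TNFα. The two tables came through in different formats, however, so one does not vouch for the other. This objection stands in part: the text cannot show whether the slip is in the source, and the source PDF has to be checked.

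**The intent is recoverable.** Table 5 is in the same section with the same drug and number. Section 4.7.7 directs vasopressors for hypotension in capillary leak syndrome, which it reports as accompanying CRS in three patients, and gives no dose cap. Section 4.8 permits supportive therapies in general. The bullet itself allows vasopressors as needed. This stands, and it is why the point is minor.

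**Stronger readings that the documents do not support.**
- A reader might infer that the protocol forbids ordinary norepinephrine doses, or that giving them would be a protocol deviation. No section says so, and Sections 4.7.7 and 4.8 point the other way.
- A reader might infer that a patient above 20 ng/min leaves the mild row and must have the infusion stopped. The row's entry criterion uses the low-dose category, which Table 5 defines, and not the figure in the bullet.
- A reader might add mismatch factors for vasopressin or combination regimens, using Table 5's rows "Vasopressin + norepinephrine equivalent of" (10 micrograms/min) and "If on combination vasopressors (not vasopressin" (norepinephrine equivalent of 20 micrograms/min). The bullet quantifies norepinephrine only and mentions neither regimen, so those factors extend it beyond its text.

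None of these objections yields a reading in which 20 ng/min is an intended limit.

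**Conclusion.** The inconsistency holds for norepinephrine monotherapy. As the text reads, the Table 6 limit is 1000 times lower than the Table 5 low-dose boundary, in the row written for low-dose vasopressors. Severity is minor. What remains is a dose limit in a CRS treatment instruction that contradicts the definition beside it.

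The documents do not say how many patients would need a vasopressor under this row, so no patient count is claimed. It would be tempting to take one from the reported rates of grade 3 infusion reactions (8% at the recommended phase II dose in Section 6.2.2; 12 of 66 in Section 6.2.3). Under Table 4, grade 3 can also be reached through hypoxia alone, so those rates do not count vasopressor use.

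The conclusion assumes that the source PDF also reads ng, and that the low-dose wording in Table 6 refers to the definition in Table 5, the only one in the protocol. If the source shows micrograms, the point falls away.

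**What to change.** Check the unit on the source page of Table 6. If it reads ng, replace the parenthesis in the mild-intervention row with a reference to low dose as defined in Table 5, which for norepinephrine alone means below 20 micrograms/min. At minimum, change ng to micrograms, which restores exact agreement for norepinephrine monotherapy.

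The cross-reference is the better choice. It leaves one definition to maintain, and it also brings in Table 5's limits for dopamine, phenylephrine, epinephrine, vasopressin and combinations, on which the bullet is silent.

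The cost is one parenthesis in one table cell, at the next amendment. Analysis, sample size and DLT rules are untouched.

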4.7.4. Other Clinically Relevant Adverse Events

If a grade 3 non-hematological adverse event occurs that is deemed by the investigator to be possibly, probably or definitely related to the study drug, then flotetuzumab will be withheld until the toxicity resolves to no more than grade 1 (mild) after which flotetuzumab may be restarted at the previously tolerated dose. If the toxicity persists for more than 14 days, then flotetuzumab will be permanently discontinued. If a grade 4 non-hematological adverse event occurs that is deemed by the investigator to be possibly, probably or definitely related to the study drug, then flotetuzumab should be permanently discontinued.

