6.2 Toxicity

6.2.1. Definition of Dose-Limiting Toxicity

DLT will be defined employing the National Cancer Institute Common Terminology Criteria for Adverse Events, Version 5.0 (CTCAE v5.0), except IRR/CRS which will be defined by the modified criteria proposed by ASCT and described in section 4.7.1 and in Table 4.

DLT is defined as:

- Grade 4 neutropenia lasting \geq 42 days from start of cycle in absence of evidence of active AML (< 5% blasts).
- The development of acute or chronic graft-versus-host disease during treatment
- Grade 3–5 nonhematologic toxicity that is possibly, probably or definitely related to the study drug

EXCEPT:

- Grade 3 fatigue, asthenia, fever, anorexia, or constipation
- Grade 3 nausea, vomiting or diarrhea not requiring tube feeding, total parenteral nutrition, or requiring or prolonging hospitalization;
- Infection, bleeding, or other expected direct complication of cytopenias due to active underlying disease;
- Grade 3 or 4 tumor lysis syndrome (TLS) or disseminated intravascular coagulopathy (DIC) if it is successfully managed clinically and resolves within 7 days without end-organ damage;
- Grade 3 or 4 isolated electrolyte abnormalities (i.e., those occurring without clinical consequence) that resolve, with or without intervention, to Grade 2 levels in < 72 hours will not be considered DLT.
- Grade 3 CRS/IRR that is successfully managed and resolves within 72 hours, as this is an expected event that does not require permanent treatment discontinuation
- Any non-leukemia-related death occurring within 90 days of treatment initiation

Treatment discontinuation for adverse events prior to the completion of one cycle will be considered a DLT unless the adverse event is disease progression, which necessitates alternative therapy, or the adverse event is not possibly, probably, or definitely due to the study treatment. Patients who discontinue treatment prior to the completion of one cycle for progressive disease or due to an event that is not possibly, probably, or definitely due to the study treatment will be replaced.

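### For Grade 4 CRS that settles within 72 hours, and for a related Grade 4 organ toxicity within a CRS episode, the protocol gives no single clear rule on restarting flotetuzumab

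*Combined protocol and SAP*

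**What the plan says.** **Section 4.7.1.** The text before Table 6 sends all infusion reactions to that table: "IRR/CRS should be managed as described below. Every attempt should be made to continue the infusion during management of the reaction". The life-threatening row stops the infusion and then instructs: "Resume the infusion at previously tolerated dose once the infusion reaction has resolved or decreased to Grade 1". The same row sets a limit: "Discontinue the infusion if not resolved to Grade 1 within 72 hours". The note to Table 4 adds: "Organ toxicities associated with CRS may be graded according to CTCAE v5.0 but they do not influence CRS grading".

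**Section 4.7.4.** The heading is "4.7.4. Other Clinically Relevant Adverse Events". The trigger is: "If a grade 4 non-hematological adverse event occurs that is deemed by the investigator to be possibly, probably or definitely related to the study drug". The consequence reads: "definitely related to the study drug, then flotetuzumab should be permanently discontinued". CRS and IRR are not excepted. For related Grade 3 events the section allows a restart at the previously tolerated dose after recovery to Grade 1 or less, with permanent discontinuation if the toxicity lasts more than 14 days.

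**Section 6.2.1.** Related nonhematologic toxicity of Grade 3 to 5 is a DLT, with listed exceptions. One exception is Grade 3 CRS/IRR that is managed and resolves within 72 hours, "as this is an expected event that does not require permanent treatment discontinuation".

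**Section 6.2.2.** This says that infusion reactions may require interruption or discontinuation, and refers to Section 4.5.1 for how. Section 4.5 has no subsections.

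**The concern.** Grade 4 CRS is among the most serious reactions the protocol prepares for, and staff would have to act on it within hours. A clinician who looks in Table 6 finds an instruction to resume. A clinician who looks in 4.7.4 finds an instruction to stop for good. Nothing states which section prevails.

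The first stake is safety: two similar patients could be handled in opposite ways on re-exposure. The second is interpretation. In a trial of at most 16 patients, whether one patient goes back on drug changes that patient's later exposure, and with it the toxicity, GVHD and response data that follow.

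**Working it through.** The plan states no figure on this point, so the main check is a comparison of the passages.

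**1. Which patients are affected?** The definition of the life-threatening row cannot be seen in the text available, so its exact content is not assumed here. The row above it ends at low-dose vasopressors and oxygen up to 6 L/min, and the row below is death. ASTCT Grade 4 in Table 4 (multiple vasopressors, or positive-pressure support) most naturally falls in the life-threatening row. ASTCT Grade 3 may fall there too.

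| Situation | Table 6, life-threatening row | 4.7.4, if it applies | Do they differ? |
|---|---|---|---|
| Grade 3 CRS, Grade 1 within 72 h | Resume | Restart allowed | No |
| Grade 3 CRS, not Grade 1 by 72 h | Discontinue | Withhold; permanent stop after 14 days | Yes, on the time limit |
| Grade 4 CRS, Grade 1 within 72 h | Resume | Permanent stop | **Yes, on re-exposure** |
| Grade 4 CRS, not Grade 1 by 72 h | Discontinue | Permanent stop | No |
| Related CTCAE Grade 4 organ toxicity in a CRS episode that reaches Grade 1 within 72 h | Resume, if the row applies | Permanent stop | **Yes, on re-exposure** |

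**2. Does 4.7.4 reach CRS?** Its wording covers related Grade 4 non-hematological events. Section 6.2.1 places its CRS/IRR exception under nonhematologic toxicity, so the protocol itself classes CRS that way. On wording alone, Grade 4 CRS is covered. On the heading and the order of sections, it is not.

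**3. Do other sections settle it?** The reason in 6.2.1 is given for Grade 3 CRS alone, which suggests without stating it that Grade 4 is treated differently. The reference in 6.2.2 leads nowhere. Section 4.11 lists unacceptable adverse events as a reason to stop but does not define them.

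**4. Does the MTD decision change?** Related Grade 4 CRS meets the DLT rule in 6.2.1, and the CRS exception covers Grade 3 only. The exceptions that can reach Grade 4 are tumor lysis or DIC without end-organ damage, isolated electrolyte changes, and complications of cytopenias from the leukemia. None describes an organ toxicity of CRS. The event is a DLT whether the drug is restarted or stopped.

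**5. How often might it arise? (illustration only)** Section 6.2.3 lists no Grade 4 infusion reaction among 66 patients. The exact one-sided 95% upper bound for 0/66 is 1 − 0.05^(1/66) = 4.4%. The chance of at least one event in n patients is 1 − (1 − p)^n:

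| p | n = 10 (maximum at one dose level) | n = 16 (maximum enrolled) |
|---|---|---|
| 1% (assumed) | 10% | 15% |
| 2% (assumed) | 18% | 28% |
| 4.4% (upper bound) | 36% | 52% |

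The 66 are the phase I safety denominator, not the group treated at the recommended dose: Grade 3 infusion reactions were 12/66 (18.2%) there, against 8% at that dose. The table counts every Grade 4 CRS. The affected cases are those that also reach Grade 1 within 72 hours, which are fewer. It does not cover organ toxicity. On that, 6.2.3 lists one related Grade 4 respiratory failure (1/66, 1.5%) and does not say whether it accompanied CRS.

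**The case against.** The best answer is structural. Sections 4.5 and 4.7.1 both send infusion reactions to 4.7.1, and 4.7.4 is headed as covering other events, after the sections on CRS, neurotoxicity and tumor lysis. A specific section normally governs over a general one. The 72-hour limit in 6.2.1 matches Table 6 and not the 14 days of 4.7.4, which also suggests that CRS was meant to be handled under 4.7.1. A DLT definition is not a stopping rule, and saying that Grade 3 does not require discontinuation does not say that Grade 4 does.

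Most of this stands. A reader might infer a flat contradiction covering every life-threatening reaction, and the documents do not support that. The row's definition is not visible, it may include Grade 3, and for Grade 3 both sections allow a restart after timely recovery. Nor does every ventilated patient automatically have a second Grade 4 event under 4.7.4: Table 4 already counts ventilation within Grade 4 CRS, and its note only permits separate grading of organ toxicities.

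The objection does not supply a stated rule. It relies on a heading against operative wording that has no exception, and it leaves open a distinct related organ toxicity that an investigator does grade 4 by CTCAE during CRS. If the reference in 6.2.2 was meant for 4.7.1, that still would not say how 4.7.1 and 4.7.4 relate.

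**Conclusion.** The point holds as an unclear boundary between two sections. It concerns Grade 4 CRS/IRR that falls to Grade 1 within 72 hours, and a related Grade 4 organ toxicity within a CRS episode. It assumes that ASTCT Grade 4 belongs in the life-threatening row of Table 6, which the neighbouring rows support.

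Two stronger inferences should be avoided. The first is that the dose decision is at risk. It is not, because the event is a DLT under either reading. The second is that a patient taken off drug is lost to the CR + CRi count. The response definitions in 5.1 do not exclude such a patient. Table 3 schedules a marrow at end of treatment, adverse events are collected for at least 30 days after the last dose, and relapse and death are followed for two years. What differs is the exposure behind the outcome, not whether it is assessed.

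The probabilities above are illustrative and are not a forecast for this population. The case for a change rests on the seriousness of the reaction and the small cost of a clear rule.

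**What to change.** Reconcile the life-threatening row of Table 6, Section 4.7.4, the reason given in 6.2.1 and the cross-reference in 6.2.2. The text should state:

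- whether 4.7.4 applies to CRS/IRR, which would also settle the 72-hour and 14-day limits for Grade 3;
- whether 4.7.4 applies to a related Grade 4 organ toxicity arising within a CRS episode;
- which section prevails where both could apply.

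The sponsor and safety monitors decide the rule; this review takes no view on which is right. The cost is one or two sentences in Table 6 and 4.7.4, any matching edit to 6.2.1, and a corrected section number in 6.2.2. Sample size, DLT counting and planned analyses are unchanged.
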